11.2 Definition of Baseline for Calculating Change

The Baseline Period is from Day 1 to Day 8. The baseline for calculating change from baseline will be defined in the following table.

Metric	Baseline	Corresponding post-baseline visits
Quit Attempts and Quitting Intentions	Day 1 (Visit 2)	Day 36 (Visit 7)
Fagerstrom Test for Cigarette Dependence (FTCD)	Day 8 (Visit 3)	Day 36 (Visit 7)
BOE	Day 8 (Visit 3)	Visits 4, 5, 6, 7
CPD daily tracking from IVRS	The average of available data from Day 2 through Day 8	Daily CPD Day 9 to 36 or the average of last week at Visits 4, 5, 6, 7
Vital Signs	Day 8, including unscheduled (rechecked) values	Visits 4, 5, 6, 7
*see Section 11.4.3 for more details		

Rationale for the baseline choices for calculating change:

Quit attempts and intentions: Day 1 is the only one measurement in baseline.

FTCD: There are 2 measurements in the baseline, Day 1 and 8. Day 8 is selected because it is anticipated that there will be changes in CPD, a key component of the FTCD score, when adult smokers are asked to track their daily cigarette consumption. Day 1 value does not reflect this change.

BOE: Day 8 is the last of the 2 baseline values and is closer to the post-baseline values.

CPD daily tracking: The weekly average was selected to adjust for the daily variability and also because total NNAL (primary end-point) has a longer half-life and the average CPD might be better representative of changes in exposure to total NNAL than the individual values.

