11.3 Criteria for Evaluation

11.3.1 Primary Endpoint

The primary outcome measure or endpoint is differences in the percent change from Baseline to the EOS in urinary total NNAL between Test and Control Groups.

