11.3.2 Secondary Endpoints

The secondary outcome measures or endpoints are:

- Differences in all BOE during the Baseline Period between Day 1 (weekly recall) versus Day 8 (daily tracking using IVRS).
- Difference in CPD during the Baseline Period between once weekly recall (Days 1 and 8) versus daily tracking (average of recordings on Days 2 through 8).
- Differences in the percent change from Baseline to EOS in BOE (urinary NE, S-PMA, blood COHb, exhaled CO) and CPD between the Test and Control Groups.
- Differences from Baseline to EOS in all BOE and CPD between the Test and Control Groups.
- Proporation of subjects in subgroups based on cigarette consumption change from Baseline to EOS (no change, <50% reduction, 50% reduction, 100% reduction, increase) within and between the Test and Control Groups.
- Proporation of subjects in subgroups based on total NNAL change from Baseline to EOS (no change, reduction, increase) within each group.
- Changes from Baseline (Day 8) to EOS in total scores of Fagerstrom Test for Cigarette Dependence (see Appendix 1), within and between the Test and Control Groups.
- Changes from Baseline (Day 1) to EOS on the Quit Attempts and Quitting Intentions, within and between the Test and Control Groups.

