11.4.1 Statistical Analyses of Primary Endpoint

A linear mixed model for repeated measures analysis of variance will be used for the analysis of the primary outcome measure. SAS procedure Proc Mixed will be used for the statistical computing. The null hypothesis is that smokers allowed *ad libitum* use of VBM-FG2 discs (test) will not differ in the primary biomarker (percent change from baseline to EOS in urinary total

NNAL) compared to smokers not allowed use of VBM-FG2 discs (control). The alternative hypothesis is that smokers allowed *ad libitum* use of VBM-FG2 discs will differ in the primary biomarker compared to smokers not allowed use of VBM-FG2 discs. The model will include percent (or absolute) change from baseline to EOS in urinary total NNAL as a response variable, product, visit, and product by visit interaction as fixed effects; and subject as random effect. In the expanded model, several additional factors will be considered. Details about the models are as follows:

Model 1:

Percent (or absolute) change from baseline in total NNAL = study group + visit + study group*visit + subject + random error

Model 2:

Percent (or absolute) change from baseline in total NNAL = study group + visit + study group*visit + subject + CPD + sex + race + body mass index (BMI) + age + random error

where

CPD = fixed covariate representing average number of cigarettes per day for past week from IVRS

study group = fixed effect term (test or control)

sex = fixed effect (male or female)

race = fixed effect (White or Non-White)

BMI = fixed effect covariate

age = fixed effect covariate (continuous)

visit = fixed effect term representing days (ordinal categorical variable)

subject = random subject effect

baseline = Total NNAL measure at Day 8

If the study group*visit interaction term is not statistically significant (P-value > 0.10), then the interaction term will be removed from the model and all comparisons will be done using the overall product means. If the interaction effect is significant (P-value < 0.10), then the comparisons will be conducted for each study visit. Comparisons between products will be done based on 5% level of significance.

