Least squares mean and standard error for the product effect will be estimated by study group and visit with P-values. P-values will also be provided for other effects in Model 2. While group comparison will be made on multiple visits in the model, the difference in change from baseline to the last visit will be the primary comparison and other comparisons will be secondary.

The models will be applied on both the mITT and the Per-protocol populations.

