11.4.2 Statistical Analyses of Secondary Endpoints

Difference in baseline:

Paired T Test will be used to examine the difference in all 5 BOEs between Day 1 and Day 8.

Paired T test will also be used to examine the differences in CPD between the once weekly recall at Day 8 (from questionnaire) and the average daily tracking of CPD from Days 2 through 8 (from IVRS).

Difference in change from baseline:

Linear mixed model for repeated measures analyses of variance will be used for the analyses of the secondary outcome measures: percent change from baseline and absolute change from baseline in all other BOEs. The same model will be used for percent change from baseline and absolute change from baseline in CPD and Total score of FTCD, the model details are as follows:

For other BOEs:

Model 1:

Percent (or absolute) change from baseline = study group + visit+ study group*visit + subject + random error

Model 2:

Percent (or absolute) change from baseline = study group+ visit+ study group*visit + subject + CPD + sex + race + BMI + age + random error

For CPD and Total Score ofFTCD:

Model 1:

Percent (or absolute) change from baseline = study group+ visit+ study group*visit +subject+ random error

Model 2:

Percent (or absolute) change from baseline = study group+ visit+ study group*visit +subject+ sex + race + BMI + age + random error

where

CPD = fixed effect covariate representing average number of cigarettes per day for the past two days from IVRS

study group = fixed effect term (test or control)

sex = fixed effect (male or female)

age = fixed effect covariate (continuous)

race= fixed effect (White or Non-White)

BMI = fixed effect covariate (continuous)

visit= fixed effect term representing days (ordinal categorical variable)

subject = random effect

baseline = Day 8 value for BOE and average of Day 2 to 8 for CPD (IVRS)

If the study group*visit interaction term is not statistically significant (P-value > 0.10), then the interaction term will be removed from the model and all comparisons will be done using the overall product means. If the interaction effect is significant (P-value < 0.10), then the comparisons will be conducted for each study visit.

Least squared mean and standard error for the product effect will be estimated by study group and visit with p-values for statistical significance. P-value will also be provided for other effects in the model.

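### A pre-test of the group-by-visit interaction at 0.10 decides whether the primary NNAL result is the last-visit difference or an average over four visits

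*SAP*

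**What the plan says.** SAP 11.3.1 gives the primary endpoint as "differences in the percent change from Baseline to the EOS in urinary total NNAL between Test and Control Groups". The null hypothesis in 11.4.1 is also framed as change to EOS. Near its end, 11.4.1 states that "the difference in change from baseline to the last visit will be the primary comparison and other comparisons will be secondary".

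Between these statements, 11.4.1 sets a rule for the model. When the test of the group-by-visit interaction gives a P-value above 0.10, "the interaction term will be removed from the model and all comparisons will be done using the overall product means". Visit-by-visit comparisons are made only when the interaction P-value is below 0.10. The rule makes no exception for the primary comparison.

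The same section promises by-visit output: "Least squares mean and standard error for the product effect will be estimated by study group and visit with P-values".

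Section 11.4.2 repeats the rule for the secondary endpoints ("all comparisons will be done using the overall product means"), although 11.3.2 also defines these as change to EOS: "Differences in the percent change from Baseline to EOS in BOE (urinary NE, S-PMA, blood COHb, exhaled CO) and CPD".

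**The concern.** Once the interaction is removed, the model has a single group difference shared by all visits. The primary comparison named in 11.4.1 can no longer be estimated from it: a contrast labelled Visit 7 would be the pooled contrast under another name, and the by-visit least squares means would show the same group difference at every visit. An analyst must either set the removal rule aside or report something other than the declared primary comparison.

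A non-significant interaction does not show that the effect is constant, and the SAP gives no power for that test. Section 11.2 says that "total NNAL (primary end-point) has a longer half-life", which makes an effect that builds over the four weeks plausible, although the SAP gives no time course. The pooled figure understates the EOS effect if the effect builds up, overstates it if the effect wanes, and is unbiased only if the effect is constant.

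At stake are the estimate, confidence interval and P-value labelled primary. The descriptive SDs by visit are not affected.

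**Working it through.** The SAP states no power or sample-size calculation (section 8), so there is no planned figure to reproduce.

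**Inputs from the SAP.** 90 Test and 60 Control (section 6). Four post-baseline BOE visits, Visits 4 to 7 on Days 15, 22, 29 and 36 (sections 6 and 11.2). Random subject effect, interaction threshold 0.10 and 5% level (11.4.1).

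**Assumptions, none from the SAP.** SD of percent change 40 points at each visit, equal within-subject correlation r of 0.5 to 0.7 between visits, complete data, and the effect profiles below.

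**Step 1: what the reduced model estimates.** With complete data, the group coefficient without the interaction is the mean of the four visit differences. In one simulated data set (SD units) these were +0.039, -0.269, -0.392 and -0.399. Their mean is (0.039 - 0.269 - 0.392 - 0.399)/4 = -0.255. The reduced model returned -0.255; the model with the interaction returned -0.399 at Visit 7.

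**Step 2: precision.**
- Visit 7 difference: SE = 40 × sqrt(1/90 + 1/60) = 40/6 = 6.67 points.
- Four-visit average: SE = 6.67 × sqrt((1 + 3r)/4). At r = 0.5 this is 6.67 × sqrt(0.625) = 5.27; at r = 0.7 it is 6.67 × sqrt(0.775) = 5.87.
- The Visit 7 interval is wider by 1/sqrt(0.775) = 1.14 to 1/sqrt(0.625) = 1.26.

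**Step 3: build-up profile.** For a step change in exposure at Day 8 and half-life h, the fraction reached after t days is 1 - 0.5^(t/h), at t = 7, 14, 21 and 28.
- h = 10: 0.384, 0.621, 0.767, 0.856; mean 0.657; mean/last = 0.767.
- h = 14: 0.293, 0.500, 0.646, 0.750; mean 0.547; mean/last = 0.730.
- h = 18: 0.236, 0.417, 0.555, 0.660; mean 0.467; mean/last = 0.708.

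For a true Visit 7 effect of -20, the pooled model therefore targets -15.3, -14.6 or -14.2.

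**Step 4: the rule in operation.** 200,000 simulated trials per scenario; interaction F-test on 3 and 444 df, term dropped if P > 0.10; average tested on 148 df, Visit 7 contrast with Satterthwaite df. Ranges run over r, and over h for build-up.

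| True profile | Term dropped | Rule's 95% CI covers Visit 7 effect | Other results |
|---|---|---|---|
| Builds to -10 | 74%-83% | 91%-93% | |
| Builds to -20 | 30%-60% | 87%-92% | In dropped trials: mean -14.1 to -15.4, coverage 80%-88% |
| Wanes evenly, -10 at Visit 4 to 0 at Visit 7 | 50%-66% | 87%-90% | Rejects in 9.5%-12.6% of trials with no Visit 7 difference |
| Constant -20 | 90% | 94%-95% | No bias; power 91%-95% against 85% with the term kept |
| No effect at any visit | 90% | 94%-95% | Rejects in 5.4%-5.8% |

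With the interaction always kept, coverage is 95% in every row, and rejection is 5% when the Visit 7 difference is zero.

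**The case against.** - **The two statements in 11.4.1 can be reconciled.** The last-visit sentence could be read as naming the primary visit only in the branch where visits are compared separately. That removes the literal contradiction, but the primary quantity then still depends on the pre-test.
- **The waning example does not fit the assumed kinetics.** This is right for NNAL. Even if exposure returned fully to the control level on Day 15, a 10-point difference would leave 10 × 0.5^(21/10) = 2.3 to 10 × 0.5^(21/18) = 4.5 points at Day 36. That row shows what the rule can do and is not a forecast. With no effect at any visit the inflation is slight.
- **The average loss is moderate.** Over all build-up trials the bias is about 1 to 2 points. Root mean square error at a true -10 is 6.2 to 6.8 under the rule against 6.7 with the term kept; at -20 it is 7.1 to 7.4 against 6.7. Power at -20 is similar (82% to 86% against 85%). These figures stand and limit the size of the harm.
- **This is a pilot.** Its main product is variability for sizing a pivotal study, and the by-visit SDs survive. However, 11.4.1 still sets a primary hypothesis and a 5% test, and the quantity to be planned for is the change to EOS.
- **The secondary endpoints have no last-visit declaration, and one objective in 5.3 speaks of four weeks.** That objective also says Baseline to EOS, as does 11.3.2, so the point extends to them.

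**Conclusion.** The concern holds and should be corrected before analysis. The conflict between the removal rule and the declared last-visit comparison follows from the SAP's own text and needs no numerical assumption. When the interaction P-value exceeds 0.10, the result labelled primary describes an average over Days 15 to 36 instead of EOS.

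The size of the error does rest on assumptions. For a build-up to -20 points, the dropped trials report about 5 to 6 points too little on average, and overall coverage falls from 95% to between 87% and 92%. For a constant effect there is no bias. The four-visit average is exact only with complete data; with missing visits it becomes a weighted average over the same visits.

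**What to change.** In SAP 11.4.1, delete the sentence that removes the interaction when P > 0.10. Keep study group by visit in Models 1 and 2 whatever its P-value, and report the Visit 7 group difference with its 95% confidence interval as the primary result in every case. Give the interaction P-value and the all-visit average as secondary results.

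In 11.4.2, make the same change for the EOS comparisons of the other BOEs and CPD. FTCD has only one post-baseline visit (11.2), so it has no group-by-visit interaction to test and the rule cannot apply.

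The change needs SAP wording and one model statement, and no new data. The real cost is precision: the wider Visit 7 interval, and lower power if the effect truly is constant, as shown above.

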11.4.2 Statistical Analyses of Secondary Endpoints

Difference in baseline:

Paired T Test will be used to examine the difference in all 5 BOEs between Day 1 and Day 8.

Paired T test will also be used to examine the differences in CPD between the once weekly recall at Day 8 (from questionnaire) and the average daily tracking of CPD from Days 2 through 8 (from IVRS).

Difference in change from baseline:

Linear mixed model for repeated measures analyses of variance will be used for the analyses of the secondary outcome measures: percent change from baseline and absolute change from baseline in all other BOEs. The same model will be used for percent change from baseline and absolute change from baseline in CPD and Total score of FTCD, the model details are as follows:

For other BOEs:

Model 1:

Percent (or absolute) change from baseline = study group + visit+ study group*visit + subject + random error

Model 2:

Percent (or absolute) change from baseline = study group+ visit+ study group*visit + subject + CPD + sex + race + BMI + age + random error

For CPD and Total Score ofFTCD:

Model 1:

Percent (or absolute) change from baseline = study group+ visit+ study group*visit +subject+ random error

Model 2:

Percent (or absolute) change from baseline = study group+ visit+ study group*visit +subject+ sex + race + BMI + age + random error

where

CPD = fixed effect covariate representing average number of cigarettes per day for the past two days from IVRS

study group = fixed effect term (test or control)

sex = fixed effect (male or female)

age = fixed effect covariate (continuous)

race= fixed effect (White or Non-White)

BMI = fixed effect covariate (continuous)

visit= fixed effect term representing days (ordinal categorical variable)

subject = random effect

baseline = Day 8 value for BOE and average of Day 2 to 8 for CPD (IVRS)

If the study group*visit interaction term is not statistically significant (P-value > 0.10), then the interaction term will be removed from the model and all comparisons will be done using the overall product means. If the interaction effect is significant (P-value < 0.10), then the comparisons will be conducted for each study visit.

Least squared mean and standard error for the product effect will be estimated by study group and visit with p-values for statistical significance. P-value will also be provided for other effects in the model.

All secondary and exploratory analyses will be conducted on the Per-protocol population only.

A linear regression analysis will be conducted within each group at each timepoint to examine the relationships between levels of all 5 BOEs (dependent variable) with either weekly cigarette counts (Day 1 and 8 from questionnaire) or daily cigarette counts (from IVRS) (independent variable). For total NNAL, the corresponding daily cigarette counts from IVRS will be the average of past 7 days. For other biomarkers, it will be the average of past 2 days. The regression analysis will be conducted on the Per-protocol population.

The proportion of subjects in subgroups will be provided with proportion and sample size based on:

- 1) Cigarette consumption change from Baseline (average of Days 2 to 8 from IVRS) to the last week (no change, <50% reduction, 2::50% reduction , 100% reduction, increase);
- 2) Total NNAL change from Day 8 to the last visit (no change, reduction, increase);
- 3) Total scores of FTCD change from Day 8 to the last visit (increase, no change, decrease)
- 4) Proportion of subjects in subgroups based on Changes from Baseline (Day 1) to EOS (increase, no change, decrease) on the change in Quit Attempts from Day 1 to last visit.
- 5) Proportion of subjects in subgroups based on Changes from Baseline (Day 1) to EOS (yes to no, no to yes, and same) on the change in Quitting Intentions from Day 1 to last visit.

The Mantel-Haenszel Chi-Square Test will be used for (1), (2), (3), and (4); Fisher exact test will be used for (5) to test the frequency differences between the two groups.

Additional statistical analyses:

Wilcoxon signed rank test will be used to test the FTCD score difference between the 2 baseline measures (Visit 2 and 3) for the test group. If there is no statistical significance, the average score will be related to the average amount of VBM-FG2 in the past week via linear regression. Otherwise the FTCD score for Visit 3 will be used.

For the test group only, a simple linear regression model will be used to examine the relationship between COHb and Exhaled CO at each post-baseline visit.

A stepwise multiple linear regression model will also be used to examine the relationship between each of the 5 BOEs (response variable) and a number of factors including average CPD, average VBM-FG2 use, average use of other products, age, sex, BMI and race at each post-baseline visit for the test group only. The average amount of tobacco product use will be for the past 7 days when total NNAL is the dependent variable and will be for the past two days when other BOE is the dependent variable.

Demographics and Characterization of Tobacco Product Use and Exposure Patterns

Demographic baseline characteristics will be summarized by study group with descriptive statistics. For continuous data, descriptive statistics will include N, mean, median, SD, min, max, coefficient of variation (CV%), and 95% confidence interval (CI). For categorical data, frequency counts and percentages will be presented. Fisher's exact test will be used to test for the differences in categorical variables (sex, race: White versus Non-white, quit attempt, cigarette consumption per day: ≤ 20 and > 20) between the 2 study groups and t test, to test for the differences in continuous variables (age, body weight, height, BMI, Number of times stopped smoking cigarettes for 24 hours or longer in an attempt to quit in past 6 months, Number of years smoked since turning 21 years).

Descriptive statistics will be provided to summarize the use of all tobacco products including cigarettes, VBM-FG2 discs and other products by study group and visit. The mean for each variable will be plotted by study group over time.

For subjects in the test group, a simple linear regression model will be used to examine the relationship between visit average of CPD (from IVRS) and visit average of VBM-FG2 use for all post-baseline visits in the study.

For subjects in the test group, a frequency table will be provided with the responses (definitely would buy and probably would buy) in the VBM-FG2 Potential Purchase Interest Questionnaire as the row variable and their average VBM-FG2 use level (4 discs versus < 4) in the last 2 visits as the column variable. Fisher exact test will be used to test for the association.

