5. PURPOSE AND STUDY OBJECTIVES

5.1 Purpose

The purpose of this study is to:

- Estimate the change in biomarkers of exposure (BOE) in adult smokers using VBM-FG2 versus adult smokers not using VBM-FG2.
- Determine the appropriate cigarettes per day (CPD) reporting method for baseline measurements (for interactive voice response system [IVRS] Base line is defined as the average CPD recorded on Days 2 through 8).

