5.3 Secondary Objectives

The secondary objectives of this study are to:

- Compare the difference in BOE (urinary total NNAL, nicotine metabolites, S-phenylmercaptmic acid [S-PMA], blood carboxyhemoglobin [COHb], and exhaled carbon monoxide [CO]) and CPD between two methods for determining CPD during the Baseline Period:
 - Recall of average daily CPD for prior week using Past 7 Day Cigarettes Use Questionnaire (Day I).
 - Daily CPD tracking using an IVRS (7 day average of values recorded on Days 2 through 8).
- Compare the differences in percent change in urinary nicotine equivalent (NE), S-PMA, blood COHb, exhaled CO, and CPD from Baseline to EOS between adult smokers randomly assigned to Test Group (*ad libitum* VBM-FG2 use) and Control Group (no VBM-FG2).
- Compare the changes in all BOE and CPD from Baseline to EOS between Test Group and Control Group over 4 weeks.
- Characterize subgroups based on change in CPD from Baseline to EOS (no change, <50% reduction, ≥50% reduction, 100% reduction, increase) within each study group.
- Characterize subgroups based on change in total NNAL from Baseline to EOS (no change, reduction, increase) within each study group.
- Compare changes in the Fagerstrom Test for Cigarette Dependence (FTCD) from Baseline (Day 8) to EOS within and between each study group.
- Compare changes on the Quit Attempts and Quitting Intentions from Baseline (Day I) to EOS within and between each study group.

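### The Day 1 versus Day 8 biomarker t test measures change in exposure over the baseline week and cannot by itself support a choice of CPD reporting method; the regressions that could are never compared

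*SAP*

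**What the plan says.** SAP 5.1 gives as one of two purposes: "Determine the appropriate cigarettes per day (CPD) reporting method for baseline measurements". SAP 5.3 makes this a secondary objective, comparing the biomarkers of exposure (BOE) "and CPD between two methods for determining CPD during the Baseline Period", namely Day 1 recall and the Days 2 to 8 IVRS average.

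SAP 11.3.2 defines the BOE endpoint as "Differences in all BOE during the Baseline Period between Day 1 (weekly recall) versus Day 8 (daily tracking using IVRS)". SAP 11.4.2 then specifies the test: "Paired T Test will be used to examine the difference in all 5 BOEs between Day 1 and Day 8".

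Two other analyses in 11.4.2 bear on the same question:

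- A paired t test on CPD itself, comparing "the once weekly recall at Day 8 (from questionnaire) and the average daily tracking of CPD from Days 2 through 8 (from IVRS)".
- Regressions: "A linear regression analysis will be conducted within each group at each timepoint to examine the relationships between levels of all 5 BOEs", with either questionnaire or IVRS counts as the predictor. The IVRS predictor is a 7-day average for total NNAL and a 2-day average for the other biomarkers.

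SAP 11.4.2 restricts all secondary and exploratory analyses to the Per-protocol population.

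**The concern.** A urine, blood or breath level is not produced by a reporting method. It is measured in the same way on Day 1 and Day 8, so attaching recall to one day and IVRS to the other turns a comparison over time into an apparent comparison of methods.

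The SAP itself expects smoking to move during that week. In 11.2, explaining the choice of FTCD baseline, it says "it is anticipated that there will be changes in CPD, a key component of the FTCD score, when adult smokers are asked to track" what they smoke. A significant BOE difference may therefore reflect altered smoking, or time and visit effects. A non-significant one says nothing about whether either method reports CPD well.

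What is at stake is a stated purpose of a pilot whose results are meant to help plan a pivotal study. As labelled, the BOE endpoint invites a conclusion about methods that its test cannot supply.

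**Working it through.** **Plan's own figure.** There is none. The SAP gives no effect size, SD or power for this comparison, and section 8 justifies the sample size only on general pilot-study grounds.

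**What the test contains.** For subject i, let d_i = BOE_i(Day 8) − BOE_i(Day 1). The statistic is t = mean(d) / [SD(d)/√n], with null hypothesis E(d) = 0. Neither the recall count nor the IVRS count appears in it. Its distribution is therefore the same however accurate or inaccurate either method is. This follows from the formula and needs no assumption.

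**Illustration.** Document input: about 150 subjects (SAP 6). Everything else is assumed: CPD mean 17, SD 5; between-subject log-SD of BOE 0.4; within-subject log-SD 0.25; reporting-error SD as shown; two-sided 5% level (the SAP states 5% only for product comparisons); 3,000 runs per row. R² is from Day 8 BOE on each method's CPD.

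| True change in smoking | Error SD, recall / IVRS (CPD) | BOE t test rejects | R² recall | R² IVRS |
|---|---|---|---|---|
| none | 6 / 1 | 5.2% | 0.104 | 0.236 |
| none | 1 / 6 | 4.4% | 0.235 | 0.103 |
| none | 3 / 3 | 4.7% | 0.181 | 0.181 |
| −10% | 6 / 1 | 88.6% | 0.091 | 0.234 |
| −10% | 1 / 6 | 88.5% | 0.234 | 0.091 |
| −10% | 3 / 3 | 88.9% | 0.172 | 0.171 |

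The simulation standard error is √(0.05 × 0.95 / 3000) = 0.4 percentage points near 5%, and √(0.886 × 0.114 / 3000) = 0.6 points near 88.6%. Differences within each block of three rows are therefore noise. The t test responds to the change in smoking and not to reporting accuracy.

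The R² columns do respond to accuracy. As a check, random reporting error shrinks R² by var(true)/[var(true) + var(error)]. That is 25/(25+36) = 0.41 for error SD 6 and 25/(25+1) = 0.96 for error SD 1, a ratio of 0.43. The first row gives 0.104/0.236 = 0.44.

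**Formal comparison of correlations.** A second set of runs used N = 150, 2,000 runs per setting, CPD mean 18, SD 7, between-subject log-SD 0.4 to 0.6 and within-subject variation 0.25 to 0.40, all assumed:

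- Methods equally accurate, smoking down 10%: the BOE t test rejects 42% to 86%. Williams' test of the two dependent Day 8 correlations rejects 4% to 5%.
- IVRS better (error SD 1.5 against 6 to 8 CPD), smoking unchanged: the t test rejects 4% to 6% and Williams' test 57% to 97%.
- In that second case the recall slope is significant in both arms in 41% to 95% of runs, so a significant slope does not identify the better method.

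**What the planned regressions lack.** They are fitted separately for each method and within study group, although at Day 8 the assigned product has not yet been used. For nicotine equivalents, S-PMA, COHb and exhaled CO they set a 2-day IVRS average against a 7-day recall, which mixes window with method. No statistic or rule compares the two fits.

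**The case against.** The strongest reply is that the test does what 5.3 literally asks. Day 1 biomarkers follow an untracked week and Day 8 biomarkers a tracked one. Whether tracking shifts exposure is relevant to which baseline is appropriate, and the SAP never says the biomarkers must show which method is more accurate. This stands in part. The contrast is a legitimate check on exposure change, and the fault lies in its label and in any method conclusion drawn from it. Even as a check on reactivity it is limited: every subject is tracked, so there is no untracked group to separate tracking from time.

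A reader might infer three stronger things that the SAP does not support:

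- That the SAP leaves the method question unanalysed. It does not: 11.4.2 compares same-week CPD directly and regresses each biomarker on both kinds of count. What is missing is a common window, pooling and a comparison of the fits.
- That the high rejection rates after a 10% fall are false positives. Smoking has truly changed in those runs, so they are power against a real change.
- That the results will be misread. The SAP gives no interpretation rule, so this is a risk and not something it states.

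The reply is also right that the remedy has limits. Day 8 recall may be primed by a week of daily calls, and 5.3 names Day 1 recall. Correlation cannot detect uniform over- or under-reporting.

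**Conclusion.** The point holds in a limited form. The Day 1 versus Day 8 biomarker test cannot by itself inform the choice between recall and IVRS, and the analyses that could are not carried through to a comparison. The first part rests only on what the test uses. The simulated rates rest on assumed inputs and on 150 subjects, where the Per-protocol population may be smaller, and are illustrative only.

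The consequence is confined to a secondary objective. IVRS is already fixed as the CPD baseline in 5.1 and 11.2, so this result does not change that baseline, and the primary NNAL comparison is untouched. The change is still worth making, because it serves a stated purpose with data already planned for collection.

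**What to change.** 1. In 11.3.2 and 11.4.2, relabel the Day 1 versus Day 8 BOE paired test as a test of change in exposure during the tracking week, and state that no conclusion about methods will be drawn from it.
2. Extend the regression analysis in 11.4.2 at Day 8. Pool both groups and relate each BOE to Day 8 recall CPD and to the Days 2 to 8 IVRS mean, so that both cover the same 7 days. Report the difference between the two dependent correlations with a 95% CI (Williams/Steiger or paired bootstrap).
3. Keep the 2-day IVRS window for the four non-NNAL biomarkers as a sensitivity analysis.
4. State the population: Per-protocol, as 11.4.2 now requires, or all subjects with Day 8 data as a declared departure. Section 10 makes Per-protocol status depend on completing the study, so it turns partly on events after Day 8.
5. Read the result alongside the planned Day 8 recall versus IVRS mean difference, which can show a systematic gap between the methods that correlation misses.

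The cost is SAP wording and one extra table, with no new data. The possible priming of Day 8 recall should be stated as a limitation, and two similar methods may not be separated.
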